ANNEX 3. ADDITIONAL INFORMATION

None.

2. LIST OF ABBREVIATIONS

AIS	Acute Ischaemic Stroke
ASD	Absolute Standardised Difference
BI	Boehringer Ingelheim
CI	Confidence Interval
DMRP	Data Management and Review Plan
GPP	Good Pharmacoepidemiology Practice
IEC	Independent Ethics Committee
IRB	Institutional Review Board
IV	Intravenous
IVT	Intravenous Thrombolysis
mRS	Modified Rankin Scale
NIHSS	National Institutes of Health Stroke Scale
NIS	Non-Interventional Study(ies)
PS	Propensity Score
PSM	Propensity Score Matching
rt-PA	Recombinant Tissue Plasminogen Activator
SOP	Standard Operation Procedure
tPA	Tissue-type Plasminogen Activator
ZSQCC	Zhejiang Stroke Quality Control Centre

4. PURPOSE AND SCOPE

This is a complete statistical and epidemiological analysis plan for the research about what are the 1-year clinical outcomes among AIS patients who were treated with IV rt-PA within 4.5 hours of symptom onset compared with those who arrived or were admitted to the hospital within 4.5 hours of symptom onset and did not receive any reperfusion treatment in a real-world clinical setting, including the 1-year all-cause mortality and neurological functional outcomes. More detailed and explicit statistical analysis methods and procedures are presented here, especially the Propensity Score Matching method.

5. AMENDMENTS AND UPDATES

None

Proprietary confidential information © 2021 Boehringer Ingelheim International GmbH or one or more of its affiliated companies

6. RESEARCH QUESTION AND OBJECTIVE

Research question: In a real-world clinical setting, what are the 1-year clinical outcomes among AIS patients who were treated with IV rt-PA within 4.5 hours of symptom onset compared with those who arrived or were admitted to the hospital within 4.5 hours of symptom onset and did not receive any reperfusion treatment?

Primary objective:

- To compare the 1-year mortality of AIS patients treated with IV rt-PA within 4.5 hours of symptom onset versus those who arrived or were admitted to the hospital within 4.5 hours of symptom onset and did not receive reperfusion treatment.

Secondary objective:

- To compare the 1-year neurological functional outcome (as measured by Modified Rankin Scale [mRS]) of AIS patients treated with IV rt-PA within 4.5 hours of symptom onset versus those who arrived or were admitted to the hospital within 4.5 hours of symptom onset and did not receive reperfusion.

7. RESEARCH METHODS

7.1 STUDY DESIGN

This study is a non-interventional study (NIS) based on existing data. We will analyse data of AIS patients aged ≥ 18 years in China collected from the ZSQCC platform. [\[P21-04780\]](#), [\[P21-04783\]](#), [\[P21-04784\]](#), [\[P21-04779\]](#), [\[P21-04782\]](#)

Approximately 11700 AIS patients in total are recorded in the ZSQCC platform and will be analysed in this study. There were approximately 8500 AIS patients (≥ 18 years of age) who were treated with IV rt PA and 3200 patients who were admitted to the hospital within 4.5 hours of symptom onset and did not receive reperfusion treatment from Jan 2017 to Mar 2020. In the China National Stroke Registry I (2007-2008), the 12-month mortality rate for post-stroke patients was approximately 14%. [\[R21-1852\]](#) For this study, it is assumed that 1-year mortality is 12% and 15% for the rt-PA treatment cohort and the cohort who did not receive reperfusion, respectively. In total, 6069 patients with a treatment ratio 2:1 are needed to observe 855 events and to detect the difference (hazard ratio=0.79) with a 2-sided alpha of 0.05 and 90% power. In addition, considering a treatment ratio 1:1 with the same assumption described above with power of 90% at a 2-sided, 5% significant level, roughly 5400 patients are needed to observe 756 events to detect the difference.

[figure not shown]
Patients meeting the inclusion and exclusion criteria will be divided into 2 cohorts:

- IV rt-PA cohort: Patients who received IV rt-PA within 4.5 hours of symptom onset
- Non-reperfusion cohort: Patients who arrived or were admitted to the hospital within 4.5 hours of symptom onset and did not receive any reperfusion treatment

Propensity score matching (PSM) will be used to match the baseline characteristics between the above 2 cohorts. The primary, secondary outcomes, as well as baseline characteristics will be compared between the matched cohorts.

The flow of data selection for each of the 2 reporting patient cohorts is depicted in Figure 1 below.

Figure 1 Patient cohorts selected for the non-interventional study

Note: dotted lines: excluded

7.2 SETTING

In this study, AIS patient data from 80 stroke centres in the ZSQCC platform from January 2017 to March 2020 will be used.

7.3 STUDY POPULATION

No sampling will be undertaken and all patients who meet all the inclusion criteria and none of the exclusion criteria will be included.

The inclusion and exclusion criteria are listed below:

Inclusion criteria:

- Patients registered in the ZSQCC platform from Jan 2017 to Mar 2020
- ≥ 18 years of age
- Diagnosed with AIS at admission
- Arrived or admitted to the hospital within 4.5 hours of symptom onset
- If treated with IV rt-PA: received IV rt-PA within 4.5 hours of symptom onset

Exclusion criteria:

- Documented IVT contraindication except age to IV rt-PA treatment according to the SmPC
- Missing any one of the key data (age, gender, baseline National Institutes of Health Stroke Scale [NIHSS], time of symptom onset, time of hospital arrival or admission, IVT or not, time of IV rt-PA treatment)
- Received thrombolysis agents other than rt-PA (urokinase, tenecteplase, recombinant plasminogen activator, prourokinase, streptokinase)
- Received endovascular treatment
- Received IV rt-PA after 4.5 hours of symptom onset

7.4 STUDY VISITS

Not applicable.

8. VARIABLES

8.1 EXPOSURES

The exposure of this study is IV rt PA treatment within 4.5 hours of symptom onset.

8.2 OUTCOMES

8.2.1 Primary outcomes

- All-cause mortality at 1 year (mRS=6)

8.2.2 Secondary outcomes

- Functional independence (mRS 0-2) at 1 year
- Favourable clinical outcome (mRS 0-1) at 1 year
- mRS 5-6 at 1 year
- Distribution of mRS score at 1 year

8.3 COVARIATES

The covariates to be collected at baseline are as follows:

- Demographic and sociological characteristics
 - o Age
 - o Gender (male, female)
 - o Medical insurance status (urban employee basic medical insurance, urban resident basic medical insurance, new rural cooperative medical insurance, other insurance, no insurance)
- Lifestyle related characteristics
 - o Smoking status (current smoker, former smoker, never smoker)
- Stroke severity (baseline NIHSS)
- Pre-stroke mRS
- Time from symptom onset to hospital admission
- For patients in the IV rt PA cohort:
 - o Time from symptom onset to treatment
 - o Time from hospital admission to treatment
 - o rt PA dosage (dichotomised as standard dosage and low dosage)
- Comorbidities at baseline
 - o Diabetes
 - o Coronary artery disease
 - o Atrial fibrillation
 - o Prior stroke/transient ischaemic attack
 - o Hypertension
- Co-medication at baseline
 - o Anti-platelet
 - o Oral anticoagulation
 - o Lipid lowering
- Hospital level
 - o Grade 2
 - o Grade 3

Proprietary confidential information © 2021 Boehringer Ingelheim International GmbH or one or more of its affiliated companies

Other covariates including:

- Duration of hospitalization
- Reasons for not being treated with rt-PA for rt-PA non treatment group

9. DATA SOURCES

The current study will be conducted based on data from ZSQCC platform, which is a continuous comprehensive reporting system that collects approximately 100000 patient-level data from 80 stroke centres from January 2017 to March 2020.

All medical documents for consecutive acute stroke patients admitted in the stroke centre will be provided by investigators from ZSQCC. Only the de-identified scanned documents will be preserved as images in a safe information database. The local infrastructure and characteristics of each recruited centre will also be recorded.

The database includes patient demographic information, baseline clinical characteristics, indicators related to diagnosis and treatment during hospitalisation and follow-up after discharge. The platform staffs tried to follow up all discharged patients by a phone call at 1-year discharge. Telephone follow-up of the platform was conducted by platform staffs. The follow-up standards were unified, and telephone recordings were all kept. Neurologists conducted trainings at regular intervals for platform staffs and randomly checked the telephone recordings. Several studies based on this dataset were approved by the Second Affiliated Hospital of Zhejiang University Institutional Review Board (IRB) and were published in peer-reviewed journals. [\[P21-04780\]](#), [\[P21-04783\]](#), [\[P21-04784\]](#), [\[P21-04779\]](#), [\[P21-04782\]](#)

10. DATA MANAGEMENT AND SOFTWARE/TOOLS**10.1 SOFTWARE/TOOLS**

Propensity score matching (PSM) will be performed using R 4.0.5 (package: MatchIt) and other analyses will be conducted with SAS 9.4.

10.2 HANDLING OF MISSING VALUES

For comorbidities at baseline (including diabetes, coronary artery disease, atrial fibrillation, prior stroke/transient ischaemic attack, and hypertension) and co-medication at baseline (including anti-platelet, oral anticoagulation, and lipid lowering), missing values will be regarded as absence of those comorbidity and co-medication. For medical insurance status, smoking status, and hospital level, missing values will be assigned to a separate group. Medians will be imputed for missing values of Pre-stroke mRS.

10.3 HANDLING OF INCONSISTENCIES IN DATA AND OUTLIERS

Inconsistencies in Data and Outliers will be re-checked. If they are still abnormal (for example: age > 120; gender is neither male nor female), they will be removed from the analysis.

11. DATA ANALYSIS

11.1 MAIN ANALYSIS

Descriptive data regarding patient demographic, lifestyle-related, and clinical characteristics will be summarized. For categorical measures, data will include the frequency (number of patients with specific cases [n]) and percentage (%) of total study patients observed in each category (N). All variables will be summarized descriptively by tabular displays of mean, standard deviations, median, inter-quartile ranges, and ranges of continuous variables, and frequency distributions of categorical variables. When necessary, continuous variables also will be categorized into intervals, with the distribution of patients (n, N, %) for each interval provided. We will compare the baseline characteristics of the 2 treatment cohorts (patients who received IV rt-PA and patients who did not receive reperfusion treatment) through the absolute standardized difference (ASD) method, where at least 0.1 ASD will be considered a significant difference.

To account for potential confounding, the 2 cohorts will be 1:1 or 2:1 matched by baseline characteristics using the Propensity Score Matching method. The feasibility of PSM will be evaluated based on available sample size and descriptive results. If patient characteristics between the 2 cohorts are significantly different, i.e., less than 50% of patients in the IV rt PA cohort can be matched to the non-reperfusion cohort based on PSM, the study design will be re-evaluated before proceeding to analysis. The PSM aims to balance the 2 cohorts on baseline covariates. The propensity score model will include age, gender, baseline NIHSS/NIHSS categories (0-4, 5-10, 11-15, 16-21, and ≥ 22), pre-stroke mRS, medical insurance status, smoking status, hospital level, diabetes, coronary artery disease, atrial fibrillation, prior stroke/transient ischaemic attack, hypertension, anti-platelet, lipid lowering, oral anticoagulation, and time from symptom onset to hospital admission. The method of Nearest Neighbour matching will be used (a maximum caliper width equal to 0.2 of the standard deviation of the logit of the propensity score) to select the matched samples. Then we will compare the baseline characteristics of the 2 propensity-score-matched cohorts. The absolute standardized difference (ASD) between the 2 PS-matched cohorts will be calculated, where at least 0.1 ASD will be considered a significant difference. For baseline covariates that are not sufficiently balanced after PSM, they will be included in an appropriate multivariate model to adjust for those differences.

For the primary outcome, a comparison of the percentage of 1-year* all-cause mortality (mRS=6) between the 2 matched cohorts will be conducted using a Chi-square test. A Kaplan-Meier curve with log-rank test will be used to analyse the data. Cox regression models will be used to estimate hazard ratios (95% confidence interval) between the 2 matched cohorts.

For the secondary outcomes, descriptive summaries will be conducted in the PS-matched cohorts separately. For the categorical variables including functional independence (mRS 0-2), favourable clinical outcome (mRS 0-1), and mRS 5-6 at 1 year, the Chi-square test and conditional logistic regression model will be conducted. For the distribution of mRS score at 1 year, the Wilcoxon rank sum test and ordinal logistic regression model will be performed to calculate the odds ratio and 95% CI.

Proprietary confidential information © 2021 Boehringer Ingelheim International GmbH or one or more of its affiliated companies

The primary and secondary outcomes will be analysed using the same method described above in the following subgroups:

- Baseline NIHSS score (0-4, 5-10, 11-15, 16-21 and ≥ 22)
- Onset to treatment time (≤ 90 mins, 91-180 mins, and 181-270 mins)
- Age (18-80 years, > 80 years)
- rt PA dose (low dose of ~ 0.6 mg/kg, standard dose 0.9 mg/kg)

*Note: 1 year in this analysis is defined as 12 ± 1 months.

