For the purpose of this study, analyses will generally be descriptive in nature and will be conducted using SAS statistical software (version 9.3 or higher). Descriptive data regarding patient demographic and clinical characteristics will be calculated. For categorical measures, data will include the frequency (number of cases [n]) and percentage (%) of total study patients observed in each category (N). All variables will be summarised descriptively through tabular displays of mean, median, ranges and standard deviations of continuous variables and frequency distributions of categorical variables. When necessary, continuous

variables also will be categorised into intervals, with the distribution of patients (n, N, %) for each interval provided.

The statistical analysis plan for the study is summarised below. Full details of the statistical analysis will be documented in the statistical and epidemiological analysis plan, which will be finalised before the end of data extraction.

As this is a NIS based on existing data, no formal hypothesis testing or comparisons between treatment cohorts are planned.

i. Main analysis

To account for potential confounding, the study cohorts (patients who received IV rt-PA and patients who did not receive reperfusion treatment) will be 1:1 or 2:1 matched by baseline characteristics using the propensity score matching (PSM) method. Propensity score (PS) will be derived from predicted probabilities of treatment initiation. The PSM aims to balance the 2 treatment cohorts on baseline covariates. The feasibility of PSM will be evaluated based on available sample size and descriptive results. If patient characteristics between the 2 cohorts are significantly different, i.e., less than 50% of patients in the IV rt-PA cohort can be matched to the non-reperfusion cohort based on PSM, the study design will be re-evaluated before proceeding to analysis. The Nearest Neighbour method of PSM will be used to select the matched samples. All the variables listed in the covariates will be considered. Covariates including duration of hospitalization and reasons for untreated with rt-PA are only for descriptive analysis. The distribution of baseline characteristics will be presented before and after the matching process. For baseline covariates that are not sufficiently balanced after PSM, the covariates will be included in an appropriate multivariate model to adjust for those differences.

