All the data cleaning, integration, analysis will be conducted under the guidance and supervision of ZSQCC.

Greater details are documented in the NIS-DMRP.

I) LIMITATIONS OF THE RESEARCH METHODS

This is a NIS based on existing data, although PSM is used, we cannot rule out the influence of other unmeasured confounding factors. In this study, potential limitations of the study design can be listed as:

- Zhejiang is an economically advanced province in China. In this study, AIS patients who received treatment or arrived or were admitted to the hospital within 4.5 hours of symptom onset in this study will be analysed and may not be fully representative to all AIS patients in China.
- AIS patient data from the ZSQCC platform were reported by the stroke centres without external monitoring.

- The treatment adapted for AIS patients may be different among stroke centres.
- The completeness of the captured data and potential for misclassification of data could differ among stroke centres.
- Some important variables may not be collected in the database. For example, patients' education level was not available in the database.

J) OTHER ASPECTS**i. Data quality assurance**

A quality assurance audit/inspection of this study may be conducted by the investigator or by IRBs / Independent Ethics Committee (IECs) or by regulatory authorities. The quality assurance auditor will have access to the investigator's study-related files and correspondence of this study.

ii. Study records**1. Source documents**

Source documents provide evidence for the existence of the patient and substantiate the integrity of the data extracted.

2. Direct access to source data and documents

The investigator/institution will permit study-related audits, IRB/IEC review and regulatory inspection, providing direct access to all related database/documents. All source documents, including progress notes must be available at all times for review by the inspection by health authorities.

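### SAP 11.1 leaves the matching ratio and the form of NIHSS open when the 1-year outcomes already exist, and the 1:1 option cannot satisfy the plan's own 50% rule

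*SAP*

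**What the plan says.** On the ratio, SAP 11.1 states that "the 2 cohorts will be 1:1 or 2:1 matched by baseline characteristics using the Propensity Score Matching method". Protocol 9.G offers the same two ratios. Neither document says how one is chosen.

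On the score, SAP 11.1 states: "The propensity score model will include age, gender, baseline NIHSS/NIHSS categories", followed by the five bands. The slash leaves open whether NIHSS enters as a number or in bands. Protocol 9.G does not settle it.

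On feasibility, SAP 11.1 states: "The feasibility of PSM will be evaluated based on available sample size and descriptive results". If "less than 50% of patients in the IV rt PA cohort can be matched to the non-reperfusion cohort based on PSM", then "the study design will be re-evaluated before proceeding to analysis". No alternative design is named.

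On timing and control, Protocol 9.G describes an analysis plan "which will be finalised before the end of data extraction". Protocol 9.H adds: "All the data cleaning, integration, analysis will be conducted under the guidance and supervision of ZSQCC". SAP section 12 provides for a second analyst to review or repeat the approach and code. SAP section 4 describes the document as a complete plan with particular detail on matching, and section 5 lists no amendments.

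**The concern.** In a study without randomisation, the matched set determines who is compared with whom. Each combination of ratio and NIHSS form gives a different set and a different hazard ratio for death. The usual protection is to fix the match without sight of outcomes.

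Here the outcomes exist. Registration ended in March 2020 and the SAP defines one year as 12 ± 1 months, so follow-up closed at about April 2021. The protocol is dated September 2021 and the SAP was planned for April 2022. The platform that made the follow-up calls also manages the data and supervises the analysis.

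An open choice in that setting puts at risk the coverage of the confidence interval and the nominal level of the planned chi-square and log-rank tests. It also means that a reader of the report cannot tell whether the match shown was the planned one. The ratio has a second problem: one of the two options on offer cannot pass the plan's own feasibility check.

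**Working it through.** **Inputs.** SAP 7.1 and Protocol 9.E give about 8500 rt-PA and 3200 non-reperfusion patients, assumed 1-year mortality of 12% and 15%, hazard ratio 0.79, two-sided alpha 0.05 and 90% power. They require 6069 patients (855 events) at 2:1 or about 5400 (756 events) at 1:1. The 50% rule is in SAP 11.1.

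**1. The plan's own sizes.** Events = (1.960 + 1.282)² / [(ln 0.79)² × a(1 − a)], where a is the treated share.
- 1:1: 10.507 / (0.05557 × 1/4) = 757 (stated 756).
- 2:1: 10.507 / (0.05557 × 2/9) = 851 (stated 855).

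For patients, the two-proportion formula with k rt-PA patients per control gives the number of controls as [1.960√(p̄(1 − p̄)(1 + 1/k)) + 1.282√(0.15×0.85 + 0.12×0.88/k)]² / 0.03².
- 1:1 (p̄ = 0.135): 2725 controls, total 5450 (stated about 5400).
- 2:1 (p̄ = 0.13): 2030 controls, total 6090 (stated 6069).

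The stated figures reproduce closely.

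**2. Does sample size decide the ratio?** At 2:1, 6069/3 = 2023 controls are needed (63.2% of 3200). At 1:1, 5400/2 = 2700 are needed (84.4%). Both fit, so size does not force a choice.

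**3. Does the 50% rule decide it?** This assumes matching without replacement, with 2:1 meaning two rt-PA patients per non-reperfusion patient. The threshold is 0.5 × 8500 = 4250 rt-PA patients.

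| Case | rt-PA patients matched | Share of 8500 |
|---|---|---|
| 1:1, every control matched | 3200 | 37.6% |
| 1:1, at the required 5400 | 2700 | 31.8% |
| 2:1, every control matched twice | 6400 | 75.3% |
| 2:1, at the required 6069 | 4046 | 47.6% |

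Under 1:1 the rule is triggered even with perfect overlap. Under 2:1 it can be met, but a match of exactly the required size falls short. Meeting it takes 4250/2 = 2125 controls with two matches each (66.4% of 3200), or 6375 patients in all, which exceeds 6069.

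**4. Cost if the choice followed the result.** The text lists 2 × 2 = 4 specifications. At the planned counts only the two NIHSS forms at 2:1 can proceed without re-evaluation. Assume no true effect, K test statistics with common correlation ρ, and reporting of any that crosses 1.96:

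P = 1 − ∫ φ(g) [Φ((1.96 − √ρ g)/√(1 − ρ)) − Φ((−1.96 − √ρ g)/√(1 − ρ))]^K dg

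| K | ρ = 0.95 | ρ = 0.75 |
|---|---|---|
| 2 | 6.5% | 8.1% |
| 4 | 8.0% | 12.3% |

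The correlations are assumptions; the documents give nothing from which to estimate them.

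**The case against.** **The redesign clause.** A reader might infer that it allows a change of design once the result is known. The text does not support that: the trigger is a match fraction, not an outcome, and re-evaluation is placed before analysis. SAP 11.1 also describes matching, then balance, then outcomes. This objection stands, and no added error is attributed to the clause. What remains is that the replacement design is unnamed and that 1:1 leads to it with certainty on the planned counts.

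**Four free choices.** A reader might count four equally available matched sets. The 50% rule removes the two 1:1 sets unless the design is re-evaluated, so the two-specification range is the more relevant one.

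**Outcome access.** A reader might infer that outcomes were inspected, or that no separation exists. Neither can be concluded. Extraction and access arrangements may be in the NIS-DMRP, to which Protocol 9.F and 9.H refer and which is not available here.

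**Hypothesis testing.** Protocol 9.G says that no formal testing is planned, so error rates are only illustrative. That is fair, although SAP 11.1 does plan tests, and selection would also affect the confidence interval.

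**Existing safeguards.** Finalising the SAP before extraction ends does not help while the SAP itself keeps the alternatives. A second analyst could reproduce any of the specifications without objection. The descriptive results used to judge feasibility are not limited to baseline data.

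**Conclusion.** The point holds in this form. The ratio and the NIHSS form are open in the SAP, the outcomes predate it, and neither visible document requires the match to be fixed before outcomes are joined. The 1:1 option conflicts with the 50% rule at the stated counts: 37.6% is its ceiling, and it would pass only if the non-reperfusion cohort were at least half the size of the rt-PA cohort. The 2:1 option is compatible with the rule, but its required sample size on its own (47.6%) is not.

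The possible inflation is moderate: about 6.5-8% in place of 5% for two specifications, and about 8-12% for four. It rests on assumed correlations of 0.95 to 0.75 and on deliberate or unconscious selection, of which there is no evidence. The cohort counts are approximate and come before the caliper is applied, so the achieved match rates will be lower than the ceilings shown.

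**What to change.** 1. In SAP 11.1 (and Protocol 9.G for the ratio), name one primary ratio and one form of NIHSS. 2:1 is the only ratio compatible with the 50% rule as written. Report the other ratio and the other NIHSS form as sensitivity analyses.
2. Reconcile the 50% rule with the ratio. Either require at least 2125 non-reperfusion patients with two matches each (4250 rt-PA patients, if the eligible cohort is 8500), or restate the rule as a share of the non-reperfusion cohort. Name the fallback analysis if it fails.
3. Run eligibility, scoring, matching, balance checks and any re-evaluation on an extract without mRS, death or follow-up fields. State that the descriptive results used for feasibility are baseline only.
4. Freeze and date the list of matched IDs, then join the outcomes. If the NIS-DMRP already provides for this, cite it in the SAP.

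The cost is SAP and protocol wording and a two-step extract of existing data. The analysts also lose the freedom to change the primary match afterwards.
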